## Chapter 5: Eligibility

In order to participate in the study, all subjects must meet the following criteria at Visit 1:

Age at baseline examination	7 to 11 years of age, inclusive
Spherical component of refraction	-0.75 to -5.00 D in each eye, inclusive, cycloplegic autorefraction
Astigmatism	≤1.00 DC in each eye, cycloplegic autorefraction
Anisometropia	≤2.00 D, based on spherical component
Best-corrected visual acuity (VA)	+0.1 logMAR or better in each eye at distance
VA with bifocal contact lens	+0.1 logMAR or better OU with +2.50 D add bifocal contact lenses at distance and near
Contact lens fit	The +2.50 D add soft bifocal contact lens must provide adequate movement and centration for continual wear
Compliance with atropine	Finish at least 85% of 0.01% atropine during the run-in period (see description in text)
History of vision correction	By patient report, not more than one month of gas permeable, soft bifocal, or corneal reshaping contact lens wear.
Myopia control	By patient report, not more than one month of participation in myopia control with treatments including, but not limited to, soft bifocal or orthokeratology contact lenses, atropine, bifocal spectacles
Ocular health	No eye diseases or binocular vision problems that may affect vision or contact lens wear (e.g. strabismus, amblyopia, etc.)
Ocular surgery	No previous intraocular or corneal surgery
Systemic health	No systemic diseases that may affect vision, vision development, or contact lens wear (e.g. diabetes, Down's syndrome, etc.)
Medications	No chronic use of medications that may affect immunity, such as topical or systemic use of corticosteroids
Participation	Agree to participate in the study for three years

For participants who meet the above eligibility criteria except “compliance with atropine” at the baseline visit, we will schedule a 1-week follow-up visit for atropine dispensing as well as contact lens insertion, removal, and care training. At the 1-week Visit, we will prescribe a 2-week supply of 0.01% atropine and give instructions on how to use the eye drops and the side effects of atropine. The participants will be asked to use atropine for 2 weeks (**run-in period**) and then return to clinic to determine final eligibility. We will weigh the atropine with its bottle before giving it to the participant, and ask the participants to bring the remaining atropine to the clinic at the 3-week Visit. We will weigh the remaining atropine with its bottle, and subjects who finish at least 71% of the atropine eye drops based on the weight during the run-in period (missing drops no more than 2 days per week on average) will be eventually enrolled in the study.

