attainable visual acuity. We will also measure each of the visual acuity measures with habitual contact lenses and spherical over-refraction in place at Visits 3 through 9 in order to compare visual acuity, while controlling for myopia progression.

We will measure the axial length, videophakometry, peripheral refractive error without contact lens, peripheral eye length, peripheral defocus with contact lens at distance, peripheral defocus with contact lens at near, pupil size, and near phoria at Visits 1, 5, 7, and 9 to determine the peripheral optical profile and the growth of the eye. We will measure accommodative lag at Visit 3 to give subjects time to adapt to their contact lenses, and at Visits 5, 7, and 9. We will perform a slit lamp biomicroscopy examination at every visit.

Compliance surveys will be completed at Visits 3 through 9 in order to determine whether compliance with contact lens and atropine is associated with myopia control effects. The potential side effects of atropine eye drops will be monitored by completing a symptom survey at Visits 2 through 9.

During Visit 1, the informed consent process requires approximately 20 minutes. The non-cycloplegic portion of the examination at Visits 1, 5, 7, and 9 requires 35 minutes. Achieving cycloplegia requires 30 minutes, and the cycloplegic portion of the examination at Visits 1, 5, 7, and 9 requires approximately 65 minutes. The CISS survey and the dilated fundus examination may be completed while waiting for cycloplegia to gain maximal effect. The total time for Visit 1 will therefore be approximately 2  $\frac{1}{2}$  to 3 hours. We help maintain subjects' interest by providing snacks and/or conducting contact lens care instruction during a follow-up visit if the subject becomes too tired to continue.

To reduce time for subjects, all secondary outcomes, except axial length, will be measured on the right eye only. We will dispense contact lenses and conduct contact lens care training at Visit 2 in order to shorten Visit 1 and to allow the subject to learn contact lens insertion, removal, and care while their eyes are not dilated.

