## Visit Windows

Visit windows are the time period during which a subject should be examined. The date of visits 2-9 are scheduled based on the date of baseline visit. All attempts should be made to examine the subject as early in the window as possible in case the subject needs to re-schedule to a later date. In order to facilitate coordination of scheduling and to set reminders, the next appointment should be made upon completion of the current appointment, even if it does not occur for six months. The visit windows are shown in Table 7-2.

Table 7-2: Visit windows for the BLINK Study.

Visit	Target Window (Day)	Acceptable Window (Days)
2	7	4-10
3	21	14-28
4	180	150-210
5	365	335-395
6	545	515-575
7	730	700-760
8	910	880-940
9	1,095	1,065-1,125

Some children may require multiple visits to learn insertion and removal of contact lenses. The subsequent visits should be scheduled as early as possible, so that Visit 3 can occur within the visit window, but after one week of wear.

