## Chapter 24: Atropine Sulfate Ophthalmic Solution (0.01%)

The source used in formulating the 0.01% atropine solution will be atropine 1% ophthalmic solution manufactured by Bausch & Lomb. The 1% atropine solution will be diluted to a final concentration of 0.01%. This compounding will be performed at Central Ohio Compounding Pharmacy located at [name], under the direct supervision of a licensed pharmacist. The atropine solution will be provided to the participants free of charge.

For participants who meet the recruitment eligibility criteria except “compliance with atropine” at the baseline visit, we will schedule a 1-week follow-up visit for atropine dispensing as well as contact lens insertion, removal, and care training. At the 1-week Visit, we will prescribe a 2-week supply of 0.01% atropine and give instructions on how to use the eye drops and the side effects of atropine. The participants will be asked to use atropine for 2 weeks (**run-in period**) and then return to clinic to determine final eligibility. We will weigh the atropine with its bottle before giving it to the participant, and ask the participants to bring the remaining atropine to the clinic at the 3-week Visit. We will weigh the remaining atropine with its bottle, and subjects who finish at least 71% of the atropine eye drops based on the weight during the run-in period (missing drops no more than 2 days per week on average) will be eventually enrolled in the study.

The parent / guardian will put one drop of 0.01% atropine in each eye of the child every night before bed, after removing the contact lenses. We ask the parent / guardian to bring the bottles to the clinic at every visit. At each visit after the enrollment (Visit 3), subjects who finish at least 70% of the atropine eye drops based on the weight will be defined as “adequate compliance with atropine” (missing drops no more than 2 days per week on average); otherwise will be defined as “inadequate compliance with atropine”.

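### The run-in atropine rule scores a share of a two-week supply, but the visit windows let the run-in last about 7 to 24 nights, so enrolment can turn on appointment dates

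*Combined protocol and SAP*

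**What the plan says.** **Run-in.** Chapter 5 (text below the eligibility table), repeated in Chapter 24, states that at the 1-week visit "we will prescribe a 2-week supply of 0.01% atropine". The bottle is weighed before dispensing and again at the 3-week visit. Enrolment goes to "subjects who finish at least 71% of the atropine eye drops based on the weight during the run-in period (missing drops no more than 2". The bracketed remark, which is the plan's explanation of the percentage, counts days in an average week. The same text asks for two weeks of use before the return visit.

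**Visit dates.** Chapter 7, Visit Windows, counts Visits 2 to 9 from the baseline date. Table 7-2 accepts Visit 2 on days 4-10 (target 7) and Visit 3 on days 14-28 (target 21). Sites are told: "All attempts should be made to examine the subject as early in the window as possible in case the subject needs to re-schedule". For children who need extra lens training, later sessions are to be booked early "so that Visit 3 can occur within the visit window, but after one week of wear".

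**Follow-up.** Chapter 24 adds: "At each visit after the enrollment (Visit 3), subjects who finish at least 70% of the atropine eye drops based on the weight" count as adequately compliant, with the same two-days-per-week explanation. The quantity dispensed for these intervals is not given.

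**Use of compliance data.** Chapter 6 has compliance surveys completed at Visits 3 to 9 "in order to determine whether compliance with contact lens and atropine is associated with myopia control effects".

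**Another threshold.** The eligibility table in Chapter 5 gives 85% for the same run-in criterion.

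**The concern.** A share of supply measures adherence only if the time available to use the supply is fixed. Here it is not. The windows for dispensing and weigh-back move independently, and no rule ties Visit 3 to the dispensing date. A low score can mean missed drops or an early appointment, and a high score can mean good adherence or a late one.

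The run-in decides who enters the single treated group of 52. Excluding adherent children costs recruits. Admitting poor adherers would tend to weaken the combination effect that Aim 1 looks for. Aim 2 uses the change in choroidal thickness to the 3-week visit, so a child whose drops ran out before a late Visit 3 may be scanned off drug.

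**Working it through.** **Inputs.** Supply of 14 nights (two weeks, nightly dosing; exact fill assumed). Threshold 71%. Visit 2 on days 4-10 and Visit 3 on days 14-28 (Table 7-2).

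**The plan's own figure.** Two missed days in seven is 5/7 = 71.4%. On the supply, 0.71 × 14 = 9.94, so 10 nights of drops are needed, and 10/14 = 71.4%. The figure reproduces at a 14-night gap, which is what target days 7 and 21 give. In whole nights the decision also agrees at 13 (3 misses pass, and 13 × 2/7 = 3.7 allows 3), but not at 12 (2 misses pass, 3 are allowed) or 15 (5 pass, 4 are allowed).

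**Range of gaps.** Shortest: 14 − 10 = 4 nights. Longest: 28 − 4 = 24 nights. If a week of lens wear follows dispensing, the shortest is about 7.

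**Scores under the rule.** Full adherence uses min(nights, 14)/14 of the supply. The least adherent child who passes has missed (nights − 10)/nights.

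| Gap (nights) | Full adherence | Result | Missed by least adherent passer |
|---|---|---|---|
| 7 | 7/14 = 50% | fail | none can pass |
| 9 | 9/14 = 64% | fail | none can pass |
| 10 | 10/14 = 71.4% | pass | 0/10 = 0% |
| 14 | 14/14 = 100% | pass | 4/14 = 29% |
| 21 | 100% | pass | 11/21 = 52% |
| 24 | 100% | pass | 14/24 = 58% |

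**Early booking at both visits.** Day 4 to day 14 is 10 nights. One missed night gives 9/14 = 64%, a fail, although 1/10 × 7 = 0.7 missed days per week is well inside the stated tolerance of 2.

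**Supply against the scan.** At a 24-night gap, nightly use empties a 14-night supply 24 − 14 = 10 nights before Visit 3.

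**Sensitivity.**
- At the 85% in the eligibility table, 0.85 × 14 = 11.9, so 12 nights are needed. Full adherence then fails at 11 nights or fewer, and the least adherent passer at 24 nights has missed 12/24 = 50%.
- With an 18-night fill, 0.71 × 18 = 12.8, so 13 nights are needed and the least adherent passer at 24 nights has missed 11/24 = 46%. The same fill makes early failure worse: 10/18 = 56% for full adherence over 10 nights.

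**Follow-up.** Gaps from Table 7-2 are 122-196 nights (Visit 3 to 4), then alternately 125-245 and 120-240. Assuming 180 nights dispensed, full adherence at the shortest gaps scores from 120/180 = 67% to 125/180 = 69%, under 70%. A child just at 70% (126 nights) at the longest gaps has missed from 1 − 126/196 = 36% to 1 − 126/245 = 49%. If supply is sized anywhere from the shortest to the longest gap, full adherence at the shortest gap scores between 100% and 50%, and the missed share at the longest lies between 30% and 65%.

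**The case against.** The best defence is that the plan does fix the run-in: it asks for two weeks of use and then a return, its target days give exactly 14 nights, and its explanation is per week. A 7-night run-in satisfies Table 7-2 only by departing from Chapter 5. That shows the intent, so it would be wrong to say the plan disregards time altogether. But the weight rule has no time term, and a site that sees the child on day 14 or day 28 is within window. The two passages need reconciling.

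The early-booking instruction also cuts both ways. Followed at both visits it gives 10 nights, where perfect adherence just passes, and it makes gaps of 21 to 24 nights less likely. It leaves no room for even one missed night, however. The 7-night floor is itself an inference from a sentence about lens wear; atropine use could run longer if lenses go home later.

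Two stronger readings are tempting and are not supported:
- *A child who misses over half the drops can pass.* That child has used at least 71% of what was dispensed. More than half of elapsed nights are missed only with a gap of at least 21 nights, the 71% threshold, little or no overfill, and every night to weigh-back counted. Against the two-week regimen alone, the least adherent passer misses 4 of 14 (29%).
- *The follow-up label is the exposure variable for the compliance question, so that analysis is blurred.* Chapter 6 assigns that question to surveys. Chapter 24 defines the weight label without giving it an analysis, and Chapter 4 gives it none either.

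**Conclusion.** The concern holds for the run-in. Within the plan's own windows the rule can reject children who meet its stated standard: every fully adherent child at gaps of 9 nights or fewer, and a child with one missed night at 10. This direction assumes only a fill of at least 14 nights. It can also admit children below the standard at long gaps, with up to 58% of elapsed nights missed under the conditions listed above. Exhaustion of the supply before the choroid scan is possible at gaps over 14 nights, by up to 10 nights, if the fill is exact and no more drops are issued.

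How many children would fall at these gaps is unknown, so neither the loss of recruits nor any dilution of Aim 1 can be sized. The follow-up label lacks the same denominator, but it excludes nobody and its error depends on an unstated supply; it is a secondary point. The change should be made because it is cheap and affects who is enrolled.

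**What to change.** 1. **Table 7-2:** date Visit 3 from the Visit 2 dispensing date, so that it agrees with the two-week run-in in Chapter 5, and state a narrow tolerance. Fourteen days after any permitted Visit 2 falls on days 18-24, inside the present window.
2. **Chapters 5 and 24:** define compliance as (bottle weight at dispensing − bottle weight at return) ÷ (expected weight), where expected weight = min(nights elapsed, nights supplied) × 2 eyes × mean drop weight. Apply the same ratio to the follow-up label, and record the quantity dispensed. The before-after difference also avoids the empty-bottle weight that a share of supply requires and the text does not mention.

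Both parts are needed. Without the cap, a fully adherent child would fail at gaps of 20 nights or more (14/20 = 70%). With it, that child scores 100% and one missed night in ten scores 90%, but 10 nights of drops in 24 still score 10/14 = 71.4%. Only the tolerance on Visit 3 removes that case.

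The 85%, 71% and 70% figures must be reconciled separately; no view is taken on which is right.

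**Cost:** less freedom in booking Visit 3, one bench measurement of mean drop weight, and recorded dispensing and return dates (Table 25-1 lists no dispensing form). No extra visits.

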### Chapter 3: Study Design

This proposed experiment is an ancillary study of a multi-center, randomized clinical trial Bifocal Lenses In Nearsighted Kids (BLINK) Study (U10EY023208), which compares myopia progression rate between subjects wearing single vision contact lenses and those wearing soft bifocal contact lenses. The BLINK Study will enroll 294 myopic children aged 7 to 11 years at two clinical centers: The Ohio State University (OSU) College of Optometry and The University of Houston College of Optometry (UHCO).

The subjects in the BLINK Study will be randomly assigned to wear either single vision soft contact lenses or soft bifocal contact lenses with either a +1.50 D add or +2.50 D add power for at least three years, with 49 subjects in each treatment arm at each clinical center. This proposed study will recruit one group of 52 additional subjects that meet BLINK eligibility criteria and that are age-matched with a comparison group -- 49 BLINK study participants who are wearing soft bifocal contact lenses with +2.50 D add power.

The subjects in this proposed study will wear soft bifocal contact lenses in combination with daily administration of 0.01% atropine for three years. The rates of myopia progression and axial elongation will be compared to those in the comparison group in the BLINK Study. The protocol for the outcome measures in this proposed project is consistent with the BLINK Study.

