## Recruitment

Recruitment methods may include, but are not limited to direct mailings to potential subjects who are likely to meet entry criteria, newspaper and/or radio advertisement, recruitment brochures, and social media. Preliminary determination of eligibility will be made during the first contact, whether in person or over the telephone. Final eligibility will be determined at the 3-week Visit after the 2-week run-in period for compliance with atropine (see details in Chapter 5).

The goal is to complete recruitment as quickly as possible. Every effort should be made to complete enrollment before the one-year deadline. The recruitment methods most likely to result in numerous visits should be utilized first. However, not all methods should be incorporated at one time because a large bolus of potential subjects could result in scheduling one to two months in advance. A new recruitment effort should be conducted as the last one to two weeks of baseline examinations are being conducted. When submitting the original IRB approval, include as many potential recruiting methods as possible because approval of amendments for recruitment may require several weeks.

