Although it has been shown that atropine eye drop has minimal side effects at the 0.01% low concentration (Chua, Balakrishnan et al. 2006; Chia, Chua et al. 2012), ocular and systemic side effects of atropine, including pupil dilation, blurred vision at distance and near, dry mouth, fever, and mental confusion will be closely monitored by surveys and objective measurements. The participants will be educated on the side effects of atropine, and be advised to stop the medication should any atropine-related adverse effects occur. The PI’s cell phone number will be provided.

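### The atropine run-in screens only the combination group, after dosing has begun, and the plan does not say how children who fail it are counted

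*Combined protocol and SAP*

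**What the plan says.** Chapter 5 sets out the run-in, and Chapter 24 repeats it. A child who meets every other criterion at baseline is given a two-week supply of drops at the 1-week visit (Visit 2). The bottle is weighed then and again at the 3-week visit (Visit 3), and "subjects who finish at least 71% of the atropine eye drops based on the weight during the run-in period" are the ones who "will be eventually enrolled in the study". The Recruitment section of Chapter 7 confirms the timing: "Final eligibility will be determined at the 3-week Visit after the 2-week run-in period for compliance with atropine". The eligibility table in Chapter 5 gives a different threshold: "Finish at least 85% of 0.01% atropine during the run-in period".

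Chapter 24 adds that participants will "be advised to stop the medication should any atropine-related adverse effects occur".

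In Chapter 3 the treated group is "52 additional subjects that meet BLINK eligibility criteria" and the comparison group is "49 BLINK study participants who are wearing soft bifocal contact lenses with +2.50 D add power". The two groups are not randomised against each other, and age is the only matching variable named.

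Chapter 4 is confined to sample size. It defines no analysis set, no denominator for side effects and no handling of run-in failures.

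**The concern.** The filter is applied after treatment has started, in one group only, and on a variable that tolerability can affect. Two things follow.

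- **Safety.** A child who stops the drops early because of a side effect can miss the threshold and so not be enrolled. If side effects are summarised over enrolled children, some of the dosed children most likely to have had a problem are missing from both numerator and denominator.
- **Aim 1.** Children shown to use and tolerate the drops are compared with lens wearers who were not screened in that way. Chapter 6 collects compliance forms to see whether compliance is related to myopia control, so the plan itself treats adherence as possibly prognostic. Age matching does not address it.

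At stake are an honest side-effect rate for the combination and a clear statement of which children the Aim 1 result describes.

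**Working it through.** **1. The plan's own figures (Chapter 4).** A two-sided paired t-test at alpha 0.05, with difference 0.33 D and SD of the paired differences 0.71 D, needs 39 pairs (power 80.7%). Fisher's z for r = 0.41 gives 44.4, against the stated 44. Then 44 x 1.18 = 51.9, or 52. These figures reproduce and are not in dispute. The 18% covers loss to follow-up only, with nothing for run-in failure.

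**2. Who can be excluded.** Taking the run-in as 14 nightly doses, with weight used proportional to doses given:

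- 71%: 0.71 x 14 = 9.94, so 10 days of use are needed;
- 85%: 0.85 x 14 = 11.9, so 12 days are needed.

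A child who doses every night and then stops for a side effect fails the 71% rule if the last dose is on day 9 or earlier, and the 85% rule if it is on day 11 or earlier. The group excluded therefore depends on which passage is followed.

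**3. Side-effect rate.** Let f be the share of starters who fail the run-in, e the side-effect rate in enrolled children and u the rate in those who fail. The rate in all dosed children is (1 - f)e + f u, so a rate based on enrolled children is too low by f(u - e). That is zero if u = e and at most f (if u = 1 and e = 0). The documents do not give f, and I assume 5% to 30%. At f = 10%, 52 / 0.90 = 57.8, so 58 starters yield 52 enrolled and 6 not. If all 6 had stopped for side effects and no enrolled child had one, the rates would be 0/52 against 6/58 = 10.3%. That is the extreme case.

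**4. Aim 1 mean.** Let d be how much faster the removed children would have progressed than those retained. The mean of the retained children differs from that of all starters by f x d. Both inputs are assumptions:

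| f | d (D) | f x d (D) | share of 0.33 D |
|---|---|---|---|
| 5% | 0.10 | 0.005 | 2% |
| 10% | 0.33 | 0.033 | 10% |
| 20% | 0.33 | 0.066 | 20% |
| 30% | 0.50 | 0.15 | 45% |

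If d = 0 there is no shift, and if d is negative the shift reverses. With no true effect, 39 pairs and SD of differences 0.71 D, a shift of 0.033, 0.066 or 0.10 D raises two-sided rejection from 5.0% to 5.9%, 8.7% or 13.8%.

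**5. Whom the result describes.** If the true effect were 0.33 D in children who pass, and those who fail got no atropine benefit, the effect over all starters would be 0.33 x (1 - f). That is 0.31, 0.30, 0.26 and 0.23 D for f = 5%, 10%, 20% and 30%. A conclusion worded for all starters would claim too much even without confounding.

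**The case against.** Much of a stronger case fails on the documents.

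- **A reader might infer that early side effects are hidden.** They are not. Subject IDs are issued when parental permission is signed (Chapter 7), before any dosing. Table 6-2 schedules the side-effect survey, pupil size and intraocular pressure at Visit 3. The adverse-event question is asked at every visit, and unscheduled-visit events are tabulated with adverse events (Chapter 26). Data will exist for children who return. Nor does any text restrict side-effect reporting to enrolled children. The gap is silence about the denominator and about children who do not return.
- **A reader might infer that Aim 1 is tilted toward the combination.** That is plausible but not documented. It needs removed children to progress faster than retained ones, and no passage says so. A parent gives the drops at bedtime, and nothing shows that two weeks of drops predict three years of a child's lens wear. Assuming that every poor lens wearer is removed and progresses as if untreated yields a large figure only by combining two extremes.
- **A reader might infer that any missed drop excludes a child.** The Chapter 5 text tolerates two missed days a week. After enrolment, low use is only labelled (Chapter 24).
- **The comparators cannot be called unselected.** BLINK's own rules are not in these documents. Only an atropine filter can be ruled out.

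What stands is the one-sided filter after dosing, the route from side effect to non-enrolment, and the missing rule for counting those who fail.

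**Conclusion.** The concern holds in a limited form. The enrolment rule can remove dosed children who had early side effects, so a side-effect rate based on enrolled children may be too low, by at most the unknown share failing the run-in. Aim 1 compares children who passed an atropine filter with children who could not have faced one. Whether this shifts the estimate, how far and in which direction cannot be determined from the documents. The range of about 0.005 to 0.15 D (2% to 45% of 0.33 D) rests wholly on assumed f of 5% to 30% and d of 0.10 to 0.50 D, and shows scale rather than an estimate. Keeping the run-in is a legitimate design choice. The remedy is reporting and wording, worth making because it is cheap and useful even if the bias is zero.

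**What to change.** Keep the run-in and add the following to Chapter 4:

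1. Define the side-effect analysis set as every child given atropine at Visit 2, including those who fail the run-in. Use the survey, pupil size and intraocular pressure already scheduled at Visit 3, plus any adverse-event reports.
2. Report how many children start the run-in, how many fail it and why, with those who do not return shown separately.
3. State that the Aim 1 conclusion applies to children who pass the run-in, and name the one-sided selection as a possible source of bias.
4. Reconcile the run-in threshold between the eligibility table (85%) and the text of Chapters 5 and 24 (71%), because it determines who is excluded.

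I would not add a sensitivity analysis restricted to comparators with good early lens wear. It would filter one group on a post-baseline form that may reflect little more than a week of wear, rely on BLINK data not described here, and break the matched pairs. With 18% loss, 49 x 0.82 leaves about 40 comparators; dropping a fifth leaves 32, below the 39 required.

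The cost is SAP wording and tabulation of data from visits already scheduled. Side-effect rates may look slightly less favourable, and the Aim 1 conclusion is narrower.
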